6. CLINICAL STUDY POPULATION

6.1. Inclusion Criteria

Subjects must meet all of the following inclusion criteria to be eligible for participation in this study:

1. Male or female subject between 18-74 years of age (extremes included), on the date of signing the ICF.
2. Documented diagnosis of pSS for <10 years prior to screening AND defined by the classification criteria ≥ 4 described by the American College of Rheumatology - European League Against Rheumatism (ACR-EULAR) (10).
3. Subject has an ESSDAI score ≥ 5 assessed on 7 domains: constitutional, lymphadenopathy, glandular, articular, cutaneous, hematological, and biological.
4. Subject has an ESSPRI score ≥ 5 .
5. Subject has stimulated whole salivary flow rate of ≥ 0.1 mL/min.
6. Subject has positive serum titers of anti-SS-A/Ro and/or anti-SS-B/La antibodies.
7. Subjects already on treatment should be on stable SoC for at least 4 weeks prior to first IP dosing.

The following SoC medications are permitted:

- Corticosteroids ≤ 7.5 mg/day (prednisone or equivalent); AND/OR
 - Non-steroidal anti-inflammatory drugs (NSAIDs); AND/OR
 - One single antimalarial at a stable dose (hydroxychloroquine ≤ 400 mg/day; quinacrine 100 mg/kg/day, or chloroquine ≤ 250 mg/day); AND/OR
 - One single immunosuppressant at a stable dose (methotrexate [MTX] ≤ 10 mg/week or azathioprine [AZA] ≤ 2 mg/kg/day); AND/OR
 - One single cholinergic stimulant at a stable dose (e.g. pilocarpine, cevimeline).
8. Subject must be able and willing to comply with the CSP requirements and must sign and date the ICF as approved by the Independent Ethics Committee (IEC) / Institutional Review Board (IRB), prior to any screening evaluations.
 9. Subject must be able and willing to comply with restrictions on prior and concomitant medication (as described in Section 6.3.2).
 10. Female subject of childbearing potential must have a negative highly sensitive (serum beta human chorionic gonadotropin or urine dipstick) pregnancy test.

11. Female subject of childbearing potential or male subject must agree to use highly effective contraception/preventive exposure measures (as described in Section 6.3.1).
12. Subject must have a body mass index (BMI) between 18-32 kg/m², inclusive.
- 13.1 Subject must be medically stable on the basis of physical examination, medical history, vital signs, 12-lead ECG, and clinical laboratory tests performed prior to first IP dosing. If there are abnormalities, they should be consistent with the underlying illness in the study population or considered not to be clinically significant in the opinion of the investigator.

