5.5. Potential Risks and Benefits

GLPG3970 has been studied in a nonclinical setting (Section 2.1) in GLP studies in rat and dogs for a duration up to 13 weeks, and is being studied in a FIH study (Section 2.2) where the single ascending dose part has been completed up to the dose of 500 mg and the multiple ascending dose part up to 400 mg q.d. GLPG3970. Study GLPG3970-CL-207 is the first study where GLPG3970 is being administered to subjects with active pSS.

[REDACTED]

[REDACTED]

[REDACTED]

In the healthy volunteers part of study GLPG3970-CL-101, single doses of 10 to 500 mg GLPG3970 and repeated doses of 100 mg q.d., 250 mg q.d., 400 mg q.d. GLPG3970 administered for 14 days to healthy subjects were well tolerated. No death or SAE occurred during the study and no TEAEs led to study drug discontinuation. For more details refer to Section 2.2 and the latest version of the IB and its relevant updates/ addenda.

The most important potential risks based on in vitro and nonclinical studies, and the healthy volunteer part of study GLPG3970-CL-101 are: QT prolongation, hemato-lymphoid system toxicity, gastrointestinal toxicity, and risks related to fertility and pregnancy (see Section 2.1). Serious infections, including opportunistic infections and tuberculosis (TB) are also considered important potential risks based on the mechanism of action of the IP.

Specific for severe acute respiratory syndrome coronavirus 2 (SARS-CoV-2) infections, risk minimization measures have been implemented in this protocol, in order to prevent recruitment of subjects with active infection and to allow prompt intervention, in case a subject is presenting with signs and symptoms of SARS-CoV-2 infection.

GLPG3970 has a novel dual mechanism of action, which is intended to restore the balance of the immune system by reducing several mediators of inflammation and by improving immune-regulatory mechanisms that may be impaired in autoimmune diseases such as, for example, pSS, RA, psoriatic arthritis, and inflammatory bowel disease. This may weaken the immune response and can potentially increase subject's vulnerability to develop infections (e.g. opportunistic infections, SARS-CoV-2, etc.). Careful monitoring and reporting of signs and symptoms is therefore required, to enable prompt medical evaluation and pharmacological or clinical intervention.

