- The dosage of corticosteroids can be increased to 10 mg/day for 3 days and must be decreased to the previous dose (<=7.5 mg/day) within 7 days.

Prohibited Medications

Prohibited medications during the study include:

- MMF within a week prior to screening.
- Cyclosporine/Tacrolimus within a week prior to screening.
- Ocular medicines (e.g. topical cyclosporine, topical NSAIDs/corticosteroids) for at least 4 weeks prior to screening, except for a sporadic use defined as a course of 7 days and no more than 2 courses during the study administered 2 weeks apart.
- Cyclophosphamide within 6 months prior to screening.
- Biologics such as, but not limited to rituximab, abatacept, and any other unapproved biologic within 6 months prior to screening.
- Any other investigational medication within 3 months or 5 half-lives of the IP, whichever is longer, prior to first IP dosing.
- Anticholinergic agents or any other medication known to cause dry mouth/dry eyes that, in the opinion of the investigator, are a contributing factor to the subject's dryness. All medications that in the opinion of the investigator are not a major factor in causing dry mouth/dry eyes can be used but must be stable for at least 4 weeks prior to first IP dosing and kept stable during the course of the study.

Other Prohibited Medications and Dietary/Herbal Products:

The following medications should be discontinued at least 2 weeks or 5 half-lives of the drug, whichever is longer, prior to first IP dosing and throughout the study.

–

■

Additional Guidance for the Use of Concomitant Medication:

— [REDACTED]
■ [REDACTED]
■ [REDACTED]
The lists provided in [Appendix 2](#) through [Appendix 6](#) are non-exhaustive.

In case of questions on concomitant medications, the contract research organization (CRO)'s medical monitor (as per study contact list) and sponsor's medical leader can be contacted.

Vaccines

Live attenuated vaccines (including live attenuated Covid-19 vaccines) are prohibited in this study from 60 days prior to screening until 6 weeks after last GLPG3970 administration. Routine household contact with persons vaccinated with live vaccine components should also be avoided.

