#### **6.1.4. Protocol Deviations and Eligibility**

Major protocol deviations are determined and recorded while the study is ongoing, and the list is finalized prior to database lock (and unblinding). For more details, please refer to the Protocol Deviations Plan.

The number (percent) of subjects with major protocol deviations will be tabulated, overall and per class of deviation, by treatment group and overall.

All available information concerning major protocol deviations, including COVID-19 related verbatim, violations on eligibility criteria and subjects not treated will be listed. Protocol deviations leading to the exclusion of subjects from any analysis set, as applicable, will be flagged.

Minor protocol deviations will not be tabulated and will be listed.

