### 6.3.3.4. Presentation of Results

No formal inferential statistics (p-values) will be derived.

Continuous parameters will be summarized by means of descriptive statistics (including 90% CI of the mean change) by parameter, treatment group and analysis window. Actual values and change from baseline will be tabulated separately.

Profile line plot by subject of all actual observed values using relative day (ADY) and profile plot on change from baseline by analysis window will be presented by treatment group. All values, including unscheduled visits will be presented in profile plot. If there is more than one visit on the same day, time will be considered to order them. Graphs of the mean (+- SE) actual values over time and of the mean (+- SE) change from baseline will be presented.

ECG will be further explored on the subset of subjects taking anti-malaria medications. Profile line plot by subject of actual observed values at baseline and at 1.5, 3 and 4.5 hours postdose will be presented by treatment group. In addition, profile line plot of the change from baseline to 1.5, 3 and 4.5 hours postdose will be presented.

The analysis of abnormalities will focus on assessments reported during the treatment period. Results reported during the screening period will only be listed.

Abnormalities of the actual values will be presented as shift tables of the worst-case abnormality versus the baseline abnormality. The table will be created per parameter, treatment group and analysis period.

A frequency table of the number (percent) of subjects with treatment-emergent worst-case abnormalities and the worst change per parameter, treatment group and analysis period will be presented.

A frequency table per treatment group and time point of the ECG interpretations as recorded in the case report form (CRF) will be provided.

A listing will be provided along with abnormality.

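### Minor, wrong as written: the permitted quinacrine dose is 100 mg/kg/day, which as a ceiling runs to grams per day and sets no effective dose limit; value and unit need confirming

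*Protocol*

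**What the plan says.** Criterion 7 in Protocol 6.1 requires subjects already on treatment to have been on stable standard of care for at least 4 weeks before first dosing, and lists what is permitted. One bullet allows a single antimalarial at a stable dose, chosen from three:

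- "hydroxychloroquine ≤ 400 mg/day"
- "quinacrine 100 mg/kg/day"
- "chloroquine ≤ 250 mg/day"

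The quinacrine figure is the same in the synopsis and under permitted medications in 6.3.2. The neighbouring limits in the list are corticosteroids ≤ 7.5 mg/day (prednisone or equivalent), methotrexate ≤ 10 mg/week and azathioprine ≤ 2 mg/kg/day. No visible text gives another quinacrine dose or a reason for dosing it by weight, and the protocol's summary of changes does not mention it.

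**The concern.** Within one bullet, two drugs have a flat daily ceiling and the third has a weight-based figure with no inequality sign. Multiplied by any adult body weight, that figure gives grams per day, against limits of 250 and 400 mg/day beside it.

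This is operative text. A subject has to meet every inclusion criterion, 6.3.2 applies the same list to concomitant medication during the study, and SAP 6.1.4 says that "violations on eligibility criteria and subjects not treated will be listed". A dose limit that cannot be used at screening cannot be used to classify deviations either. What is at stake is whether sites and deviation review had a usable quinacrine limit. No estimate or test in the analysis depends on the figure.

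**Working it through.** **Inputs from the documents.** Quinacrine 100 mg/kg/day; hydroxychloroquine ceiling 400 mg/day; chloroquine ceiling 250 mg/day; azathioprine ceiling 2 mg/kg/day (all criterion 7). Criterion 12 bounds body size: "Subject must have a body mass index (BMI) between 18-32" kg/m².

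**Assumption.** The documents give no height range. I take 1.50-1.90 m and test 1.40-2.00 m.

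**Formulas.** Weight (kg) = BMI × height². Quinacrine as written (mg/day) = 100 × weight.

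| Case | Weight (kg) | As written (mg/day) | ÷ 400 | ÷ 250 |
|---|---|---|---|---|
| BMI 18, 1.50 m | 18 × 2.25 = 40.5 | 4,050 | 10.1 | 16.2 |
| 70 kg subject | 70 | 7,000 | 17.5 | 28.0 |
| BMI 32, 1.90 m | 32 × 3.61 = 115.52 | 11,552 | 28.9 | 46.2 |
| BMI 18, 1.40 m | 18 × 1.96 = 35.28 | 3,528 | 8.8 | 14.1 |
| BMI 32, 2.00 m | 32 × 4.00 = 128 | 12,800 | 32.0 | 51.2 |

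The result stays in grams per day whichever height range is used.

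**Reverse check.** The written figure equals the hydroxychloroquine ceiling only at 400/100 = 4 kg body weight, and the chloroquine ceiling only at 250/100 = 2.5 kg.

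**Comparison with the other per-kg limit.** 100/2 = 50, so quinacrine is set 50 times higher per kg than azathioprine.

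**The missing sign.** All five other numeric limits in the list carry ≤; quinacrine does not. There are two readings:

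- As a ceiling, by analogy with its neighbours, the entry gives the ranges above. Adding ≤ and leaving the unit alone changes none of them.
- Literally, it names one exact dose, so a subject on any other quinacrine dose would fall outside the permitted list.

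Neither reading works as a threshold.

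**If 100 mg/day was meant (assumption).** The written ceiling is then too high by a factor equal to body weight in kg: 4,050/100 = 40.5 to 11,552/100 = 115.5.

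**The case against.** **The error is inferred.** The three statements agree with each other, and no visible passage gives a competing dose. The documents do not say what quinacrine doses are used in practice, so the comparison is with different drugs. This stands as a limit on certainty: the intended value cannot be recovered from the text. It does not rescue the entry, which is unusable on either reading.

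**Per-kg limits are not foreign to the list.** Azathioprine has one, so scaling by weight is not itself a sign of error. That is correct. The evidence is the size of the figure, the flat form of the other two antimalarial limits and the missing sign, taken together.

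**Other controls apply.** A reader might infer that background antimalarial therapy is unrestricted. It is not: only one agent is allowed, at a stable dose, for at least 4 weeks before dosing, and 6.3.2 asks for doses to stay as stable as possible to the end of the study. Investigators can exclude on risk, and 6.3.2 names a contact route ("In case of questions on concomitant medications"). Only the quinacrine dose lacks an effective limit.

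**Redaction.** Parts of 6.3.2 are blacked out and Appendices 2-6 are not visible. A further limit could sit there, though a different figure would then conflict with three visible statements.

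**A QT consequence is tempting.** Protocol 5.5 says the most important potential risks "are: QT prolongation, hemato-lymphoid system toxicity, gastrointestinal toxicity", among others, and SAP 6.3.3.4 says "ECG will be further explored on the subset of subjects taking anti-malaria medications". A reader might infer that the loose quinacrine limit weakens QT safety. The documents do not support that. Nowhere do they say quinacrine affects QT. The planned ECG plots cover all antimalarial users with no dose criterion, so they would run unchanged under either unit, and the ECG exclusion and stopping rules do not depend on quinacrine dose.

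**The study has stopped.** SAP section 1 reports termination on the Safety Monitoring Committee's recommendation of 26 November 2021, so a correction can no longer change who is enrolled. This stands and lowers the priority.

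**Conclusion.** The entry is wrong as written, and the point is minor. As a ceiling it permits about 4,050-11,550 mg/day over BMI 18-32 kg/m² at assumed heights of 1.50-1.90 m (about 3,530-12,800 mg/day at 1.40-2.00 m), which is 10-29 times the hydroxychloroquine limit and 16-46 times the chloroquine limit over the narrower height range. The arithmetic is firm. That the unit is the slip is the likely explanation but remains an inference from the neighbouring limits, with redacted text unchecked.

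The practical effect is small. Quinacrine use among the 30 planned subjects may be nil. Sample size, significance level, endpoints and the Full Analysis Set (all randomized and dosed) do not depend on the figure. After early termination, the correction matters only for deviation review and for any later protocol that reuses the text.

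**What to change.** Check the sponsor's source for the intended quinacrine value and unit. Then restate the entry as an explicit flat ceiling in the synopsis, 6.1 criterion 7 and 6.3.2. The likely wording is quinacrine ≤ 100 mg/day, but that figure is an assumption the documents do not confirm. Adding ≤ alone is not enough.

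For this study, record the confirmed limit where eligibility deviations are reviewed and check any subject on quinacrine against it. Correct the text before it is reused.

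The cost is a source check and one line in three places, with no change to data collection, sample size or analysis. Had enrolment still been open, the change would have needed a protocol amendment submitted to the ethics committees.

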6.2. Exclusion Criteria

Subjects meeting one or more of the following criteria cannot be selected for this clinical study:

1. Secondary Sjögren's syndrome according to the ACR-EULAR (2016) classification (10).
2. History or presence of unstable condition not related to Sjögren's Syndrome that, in the opinion of the investigator, could constitute an unacceptable risk when taking the IP or interfere with the interpretation of data.
3. Subject has any active systemic infection within 2 weeks prior to first IP dosing, or poorly controlled chronic cardiac, pulmonary, or renal disease.
4. Subject has a known or suspected history of or a current immunosuppressive condition, or a history of opportunistic infections (e.g. HIV infection, histoplasmosis, listeriosis, coccidioidomycosis, pneumocystosis, aspergillosis).
5. Subject has a chronic hepatitis B virus (HBV) infection, as defined by persistent HBV surface antigen (HBsAg) positivity. Subject has hepatitis C virus (HCV) infection, as defined by positive HCV antibody at screening and detectable HCV viremia. Subjects with positive HCV antibody must undergo reflex HCV ribonucleic acid (RNA) testing, and subjects with HCV RNA positivity will be excluded. Subjects with positive HCV antibody and negative HCV RNA are eligible.
- 6.1 Subject testing positive for SARS-CoV-2 infection as detected at screening based on real time polymerase chain reaction (RT-PCR) or at baseline based on immunoglobulin M (IgM) immunoassay, or subjects who have been in contact with SARS-CoV-2 infected individuals in the 2 weeks prior to first dosing of IP. Subjects presenting any signs or symptoms of SARS-CoV-2 infection, as detected prior to first IP dosing following careful physical examination (e.g. cough, fever, headaches, fatigue, dyspnea, myalgia, anosmia, dysgeusia, anorexia, sore throat, etc.) (11,12). In addition, any other locally applicable standard diagnostic criteria may also apply to rule out SARS-CoV-2 infection.
- 7.3 Subject has taken any disallowed therapies.
 - Mycophenolate mofetil (MMF) within a week prior to screening.
 - Cyclosporine/Tacrolimus within a week prior to screening.
 - Cyclophosphamide within 6 months prior to screening.
 - Ocular medicines (e.g. topical cyclosporine, topical NSAIDs/corticosteroids) for at least 4 weeks prior to screening, except for a sporadic use.
 - Biologics such as, but not limited to, rituximab, abatacept, and any other unapproved biologic within 6 months prior to screening.
 - Plasmapheresis within 12 weeks prior to screening.

- Plasma exchange within 12 weeks prior to screening.
 - Intravenous immunoglobulin (IVIG) therapy within 24 weeks prior to screening.
 - Other prohibited medications within 2 weeks or 5 half-lives, whichever is longer, prior to first IP dosing, as listed in Section 6.3.2.
- 8.1 Concurrent use of anticholinergic agents or any other medication known to cause dry mouth/dry eyes that, in the opinion of the investigator, are a contributing factor to the subject's dryness and/or use of anticholinergic agents not contributing to this dryness, if not stable for at least 4 weeks prior to screening (see Section 6.3.2).
9. Subject has a history of TB diagnosis or evidence of active or latent infection with *Mycobacterium tuberculosis*.
 - Positive QuantiFERON-TB Gold test result at screening, AND/OR
 - Chest radiograph (posterior anterior view) taken within 12 weeks prior to screening, read by a qualified radiologist or pulmonologist, with evidence of current active TB or inactive TB.
10. Investigator or other study staff or relative thereof who is directly involved in the conduct of the study.
11. Subject has any condition or circumstances that, in the opinion of the investigator, may make a subject unlikely or unable to complete the study or comply with study procedures and requirements (e.g. active alcohol or drug abuse).
12. Subject has a known hypersensitivity to IP ingredients or history of a significant allergic reaction to IP ingredients as determined by the investigator.
13. Subject has any condition for which, in the opinion of the investigator, participation would not be in the best interest of the subject (e.g. compromise the well-being) or that could prevent, limit, or confound the protocol-specified assessments.
- 14.2 Subject has presence or sequelae of gastrointestinal, liver, kidney (creatinine clearance <60 mL/minute, using the Cockcroft-Gault formula: if calculated result is <60 mL/minute, a 24-hour urine collection can be done), or other conditions known to interfere with the absorption, distribution, metabolism, or excretion of drugs.
15. Subject has a history of lymphoma or any malignancy within the past 5 years prior to screening with the exception of excised and curatively treated non-metastatic basal cell carcinoma or squamous cell carcinoma of the skin or carcinoma in situ of cervix which is considered cured with minimal risk of recurrence.
16. Subject concurrently participates or participated in a drug, drug/device, or biologic investigational research study within 3 months or 5 half-lives of the IP, whichever is longer, prior to the first dose.
- 17.2 Subject has a history or presence of cardiopathy, or clinically significant abnormalities detected on 12-lead ECG of either rhythm or conduction e.g. repeated demonstration of a QTcF >450 ms detected on the 12-lead ECG or a history of additional risk factors for TdP (e.g. heart failure, family history of long QT syndrome, hypokalemia and other electrolyte disorders). A first-degree atrioventricular block will not be considered as a significant abnormality.
18. History of organ or bone marrow transplant.
19. Female subject is pregnant or breast feeding or intending to become pregnant or breastfeed during the study.

20.1 Subject was vaccinated with a live attenuated vaccine within 60 days prior to screening.

21.1 Subject has severe organ manifestation or life-threatening condition, or has planned a surgery during the study.

22.2 Subject has any of the following laboratory abnormalities:

- aspartate aminotransferase (AST) >2 times the upper limit of normal (ULN)
- alanine aminotransferase (ALT) >2 times the ULN
- total bilirubin >2 times the ULN
- prothrombin time or partial thromboplastin time > ULN.
- serum potassium concentration <3.5 mmol/L

23. Subject is institutionalized by virtue of an order issued by either the judicial or the administrative authorities or has a dependency on the sponsor or investigator.

6.3. Prohibition and Restrictions

6.3.1. Precautions for Sexual Intercourse

Highly effective contraceptive measures for both males and females of childbearing potential must be documented in the source documents.

